In order to use information on test sensitivity and specificity, we must also take into account the *absolute* risk of infection in each pregnant woman during the period when she is pregnant. A ZIKV IgM+ result is more likely to be a false positive if there are few surveillance reports of ZIKV at that time; and more likely to be a DENV infection if large numbers of DENV are being reported. Estimates of the *temporal trends* in infection of ZIKV, DENV and CHIKV are available from routine surveillance sources, as noted above; to obtain estimates of the absolute risk surveillance data must be supplemented by data on the proportion of infections, whether symptomatic or not, that are reported to the surveillance center. This proportion, which will vary between ZIKV, DENV and CHIKV, can be *approximately* estimated by aligning weekly surveillance reports with data from ZIKA-VT (See *Section 8.1*).

Following reports of sexual transmission of ZIKV, ZIKA-VT will be collecting information on infection in fathers / partners. We will explore the possibility of using this information alongside surveillance data when estimating the likely timing of maternal infection.

Author: [name] (UNIVBRIS)

**17** 

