#### 8.1 Analyses to be carried out

Note that the estimates of incidence and seroprevalence that can be generated directly from ZIKA-VT are not true population estimates, because, within each collaborating center, the intention is to recruit pregnant women from areas at higher risk of arbovirus infection, and during periods of higher incidence. However, there is an interest in estimating incidence because it may correlate with risk of transmission or adverse clinical outcomes, if for example, both are related to viral load or degree of susceptibility.

All analyses will be initially stratified by center and mosquito season, or by center and year if there is no mosquito season. The text under each heading below should be understood as specifying one or more tables, in most cases separately for each of the three arboviruses.

8.1.1 Basic demographics of the sampled population. We will tabulate the numbers recruited each season, their age distribution. Further breakdowns will be by: socio-economic class, income range, type of housing, area of residence, residence stratified by arbovirus infection incidence (from surveillance data), as considered appropriate

8.1.2 Seroprevalence and cumulative incidence. For each arbovirus, the denominator for a seroprevalence estimate is the number of women who had at least one IgG test, and the numerator is the number who were IgG+ on their first test. In addition to "crude" (without adjustment) estimates of seroprevalence, we will obtain estimates of cumulative incidence  $\pi$ , which is (observed) seroprevalence p adjusted for IgG sensitivity and specificity, using the relationship

$$p = \pi Se + (1 - \pi)(1 - Sp)$$

Author: [name] (UNIVBRIS)

26

The sensitivity and specificity will be characterized as probability distributions based on the data available, assembled under the ZIKA-VID work package. The sources of this data will be continually updated (see *Appendix 4*).

If more than one test was used, results will be reported separately for each test (see Table 5)

The adjustment can be extended to account for cross-reactivity between DENV and ZIKV IgG tests, given information on sensitivity, general false positive rates, and cross-reactivity of both assays:

$$p_{Z} = \pi_{Z} S e_{Z} + (1 - \pi_{Z})(1 - S p_{Z}) + \pi_{D} X r_{Z}$$

$$p_{D} = \pi_{D} S e_{D} + (1 - \pi_{D})(1 - S p_{D}) + \pi_{Z} X r_{D}$$

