This gives us two equations in two unknowns, and allows us to estimate the true cumulative incidence of both infections  $\pi_Z$ ,  $\pi_D$  from the observed seroprevalences  $p_Z$ ,  $p_D$ .

To bring together cumulative incidence estimates from multiple tests, the above methods for correcting for sensitivity and specificity can be extended to apply to *any number of tests*, and *any number of combinations of tests* (see Appendix 6).

**8.1.3** Proportion of symptomatic infections. For each infection, the denominator is the number of infected women, and numerator is the number of those reporting symptoms (according to pre-specified criteria) who were confirmed by PCR+, IgM+, or rising IgG. Infections which may either be ZIKV or DENV will be tabulated separately. We will investigate whether the proportion of symptomatic infections for each arbovirus is related to seroprevalence of the others.

8.1.4 Seroconversions and incidence of primary infections. The denominator is the number of women who were initially IgG- and who were retested on IgG at a later date. The numerator is the number of these women who were tested IgG+ at some later date. The time at risk is the total time between the first IgG- and either the first IgG+ if there was one, or the time between the first and last IgG- tests. Incidence of primary infection is found by dividing the number of seroconversions by total time at risk.

Once again, both crude and sensitivity-specificity-adjusted estimates will be considered, and separate estimates will be derived if there is more than one IgG test, using a similar format to *Table 5*.

Associations between incidence on one arbovirus and previous infections with the same or other arboviruses will be explored

8.1.5 IgM prevalence. The denominator is the number of women who were ever tested by IgM, and the numerator is the number whose first IgM test was a +ve. Separate analyses will be performed for different IgM tests, or tests on different samples.

Sensitivity and specificity will be taken into account, as above, and so will ZIKV-DENV cross-reactivity, to give adjusted estimates of IgM prevalence for each assay. Associations between IgM prevalence on one arbovirus and previous infections with the same or other arboviruses will be explored.

Author: [name] (UNIVBRIS)

27

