8.1.6 Incidence of primary infections estimated by increase in seroprevalence. If we know or can estimate the cumulative incidence at a starting point T, then cumulative incidence at time t is related to incidence between t and T as follows:

$$\pi(t) = \pi(T) + (1 - \pi(T) \left( 1 - \exp\left( -\sum_{T \le u \le t} \lambda(u) \right) \right)$$

This can be modelled, for example assuming piece-wise constant incidence.

For DENV infection, which has been present for much longer, it may be preferable to model age-and time-specific cumulative incidence:

$$\pi(a,t) = \pi(a,T) + (1-\pi(a,T)\left(1-\exp\left(-\sum_{T \le u \le t} \lambda(a-T+u,u)\right)\right)$$

Using data from pregnant women, we would model incidence from time T and age 16 upwards.

These calculations assume that cumulative incidence can be estimated by adjusting seroprevalence for sensitivity and specificity as shown in *Section 8.1.2* 

8.1.7 Alignment with surveillance data: population estimates of incidence. Once estimates of incidence are available, they can be aligned with surveillance reports to estimate the proportion of incident infections (symptomatic or not) that are reported to the surveillance system. "Alignment" should be interpreted as putting the dates of the tests on the real timescale, so that incidence estimates for ZIKV, DENV, and CHIKV based on ZIKA-VT data can be compared to numbers of cases notified to national or regional surveillance centers, both confirmed and suspected.

If the estimated incidence in some period t is  $\lambda(t)$  and M(t) cases are reported in, say, the population of adult women aged 16-44, over the same time period and from the same area where ZIKA-VT is recruiting, then we can calculate the proportion of all infections that were reported over that time period as :

$$\theta(t) = \frac{M(t)}{N(1 - e^{-\lambda(t)})}$$

Where N is the relevant population size. This quantity can be examined over time to see if it remains relatively stable, and can be used in analyses of test persistence and adjustments for sensitivity and specificity needed to estimate the gestational age of maternal infection and vertical transmission rate (see Sections 5,7).

Further, once an estimate  $\theta(t)$  is available, it can be used to "gross-up" counts M(t), to estimate the true number of infections on a national or regional basis:  $M(t)/\theta(t)$ .

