### Table 5. Population epidemiology: estimates of seroprevalence and cumulative incidence by center and year/season, for each IgG assay

Cumulative incidence is seroprevalence adjusted for sensitivity, specificity, and cross-reactivity. The overall estimate will combine all sources of data (see *Appendix 6*).

Centre, Year/season		ZIKV	DENV	CHIKV
	Number ever IgG tested	N		
IgG test 1	Number +ve on first test	R		
	Observed seroprevalence	P=R/N (95% Confidence interval)		
	Cumulative incidence (adjusted)			
	Number ever IgG tested	N		
IgG test 2	Number +ve on first test	R		
	Observed seroprevalence	P=R/N (95% Confidence interval)		
	Cumulative incidence (adjusted)			
	Number ever IgG tested	N		
etc.	Number +ve on first test	R		
	Observed seroprevalence	P=R/N (95% Confidence interval)		
	Cumulative incidence (adjusted)			
Cumulative incidence fro	m all sources combined			

38

Author: [name] (UNIVBRIS)

Table 6. Women's follow-up study: spectrum of initial symptoms in pregnant women and not-pregnant controls, by center

Symptoms		ZI	KV			DE	NV			СН	IKV		
	Preg	nant	Ν	ot	Preg	nant	N	ot	Preg	nant	N	ot	
			preg	nant			preg	nant			preg	nant	
	N	%	N	%	N	%	N	%	N	%	N	%	
Symptom 1													Covariates in regression analyses
Symptom 2													
"													Primary vs secondary infection
"													Co-infection
Symptom combination 1													Previous infection with same or
Symptom combination 2													different arboviruses
"													
"													
Meets clinical criteria 1													
Meets clinical criteria 2													
"													
"													
No symptoms													

Author: [name] (UNIVBRIS)

39

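### Sections 8.1.4 and 8.1.6 name only sensitivity and specificity when adjusting incidence; without a ZIKV-DENV cross-reactivity term, incidence is biased upward, and IgM persistence (8.2.1) and possibly the VTR correction with it

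*SAP*

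**What the plan says.** Section 8.1 of the SAP treats cross-reactivity differently from one quantity to the next.

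- **8.1.2, IgG seroprevalence.** It starts from sensitivity and specificity, then offers an option: "The adjustment can be extended to account for cross-reactivity between DENV and ZIKV IgG tests". Two equations follow, each with a separate Xr term multiplied by the cumulative incidence of the other virus.
- **Table 5.** Its heading treats cross-reactivity as part of the adjusted estimate: "Cumulative incidence is seroprevalence adjusted for sensitivity, specificity, and cross-reactivity".
- **8.1.4, seroconversion incidence in initially IgG-negative women.** "Once again, both crude and sensitivity-specificity-adjusted estimates will be considered". It adds that "separate estimates will be derived if there is more than one IgG test, using a similar format to" Table 5. It does not mention cross-reactivity and gives no formula for adjusting a seroconversion count or rate.
- **8.1.5, IgM prevalence.** "Sensitivity and specificity will be taken into account, as above, and so will ZIKV-DENV cross-reactivity".
- **8.1.6, incidence from rising seroprevalence.** "These calculations assume that cumulative incidence can be estimated by adjusting seroprevalence for sensitivity and specificity as shown in" 8.1.2. Cross-reactivity is not named.

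Incidence is then used in two places. Section 8.2.1 divides IgM prevalence (8.1.5) by incidence from 8.1.4 or 8.1.6 to obtain mean IgM persistence. Section 8.1.7 converts incidence, without saying which estimate, into the reporting fraction theta(t). That fraction may be used in the adjustments for gestational age at infection and VTR. Sections 5.1 and 7.6 point to 8.1.7 for the absolute prior risk.

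**The concern.** A woman who is ZIKV IgG-negative at baseline and acquires DENV before her next sample may turn ZIKV IgG-positive by cross-reaction. With only sensitivity and specificity in the adjustment, she contributes a ZIKV primary infection. A fixed specificity cannot remove this, because the rate of such false seroconversions moves with DENV incidence.

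Three results are exposed:

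- **Incidence** of ZIKV primary infection, and of DENV by the mirror argument, is biased upward. The associations with other arboviruses planned in 8.1.4 are contaminated by the same route.
- **Mean IgM persistence** in 8.2.1 has a numerator corrected for cross-reactivity and a denominator that is not, so it is biased downward.
- **The VTR correction.** If this incidence enters 8.1.7, theta(t) is too small and grossed-up infection counts are too large. Too few ZIKV IgM-positive results are then treated as false, and the VTR stays too low.

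**Working it through.** **1. The plan's own dilution figures (7.6).** With IgM specificity 95% and, as the example implies, sensitivity 1, the factor by which VTR is underestimated is

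k(x) = [x + (1 − x) × 0.05] / x, where x is the true risk of infection in pregnancy.

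- x = 10%: (0.10 + 0.045)/0.10 = 1.45. The SAP says 1.5, which agrees as an approximation.
- x = 1%: (0.01 + 0.0495)/0.01 = 5.95. The SAP says 5; the arithmetic gives about 6.

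**2. Inputs for the bias.** True ZIKV risks of 1% and 10% are the SAP's examples in 7.6. IgG Se, Sp and Xr, and DENV risk during follow-up, are not given (the Appendix 4 table is empty). Assumed ranges: Se/Sp of 1/1, 0.95/0.98 and 0.90/0.95; DENV risk 1%, 5%, 10%; Xr 0.05, 0.20, 0.50. Because 8.1.4 has no formula, the proportion seroconverting is treated as p in the 8.1.2 equation.

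**3. Effect of leaving Xr out.** Generate p = πZ·Se + (1 − πZ)(1 − Sp) + πD·Xr, then invert without the last term:

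estimate = [p − (1 − Sp)]/(Se + Sp − 1) = πZ + πD·Xr/(Se + Sp − 1).

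Central case, Se = Sp = 1, DENV 5%, Xr 0.20: the added amount is 0.05 × 0.20 = 0.010, so 1% becomes 2.0% and 10% becomes 11.0%.

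**4. Effect on VTR if the estimate becomes the prior risk.** The ratio of corrected VTR to its proper value is k(estimate)/k(true).

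- 1% true risk, central case: k(0.02) = (0.02 + 0.049)/0.02 = 3.45, and 3.45/5.95 = 0.58.
- 10% true risk, central case: k(0.11) = (0.11 + 0.0445)/0.11 = 1.40, and 1.40/1.45 = 0.97.

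**5. Effect on IgM persistence (8.2.1).** Persistence scales as true/estimated incidence, approximated here by the ratio of risks: 1/2.0 = 0.50 at 1%, and 10/11 = 0.91 at 10%.

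| | True ZIKV risk 1% | True ZIKV risk 10% |
|---|---|---|
| Estimated risk without Xr, full range | 1.05% to 6.9% | 10.05% to 15.9% |
| VTR relative to proper value | 0.28 to 0.96 | 0.87 to 1.00 |
| IgM persistence relative to true | 0.15 to 0.95 | 0.63 to 1.00 |

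Solving the two 8.1.2 equations jointly, with Xr, returns the true risk in every scenario.

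**6. Sensitivity to the form of the equation.** The 8.1.2 equation adds Xr on top of the background false-positive rate. If Xr instead replaces that rate in DENV-infected women, p = I_Z·Se + (1 − I_Z)[I_D·Xr + (1 − I_D)(1 − Sp)], the bias is somewhat smaller: the ranges become 1.0% to 6.2% at 1% risk and 10.0% to 14.8% at 10%. It vanishes where Xr equals 1 − Sp. As an intermediate case, with Se 0.95, Sp 0.98, I_D 10% and Xr 0.10 to 0.50, a true 5% is estimated at 5.8% to 9.9%, so persistence is 0.86 to about 0.50 of its true value.

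**7. Can the 8.1.2 equation be used in 8.1.4 as it stands?** No. It multiplies Xr by cumulative DENV infection in all tested women. In women already negative at baseline, the relevant DENV infections are those within the test interval. With cumulative DENV of 70% (assumed) and Xr 0.20, the equation would subtract 0.70 × 0.20 = 14 percentage points from a seroconversion risk of perhaps a few percent.

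**The case against.** The strongest reply is that 8.1.4 does not exclude cross-reactivity. Its opening words refer back to 8.1.2, which contains the Xr equations, and it borrows the format of Table 5, whose heading includes cross-reactivity. The SAP sometimes uses sensitivity and specificity as shorthand for methods that contain Xr, and section 3.2 calls cross-reactivity a cause of lack of specificity. This stands as far as it goes: a reader might infer a decision to omit the term, and the text does not support that. It does not settle the matter. Section 8.1.2 and Appendix 2 keep Xr apart from Sp, 8.1.5 names it separately, and the 8.1.2 equation does not transfer (working, step 7).

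Other stronger readings also go too far:

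- **That DENV infections in general are counted as ZIKV.** Only the fraction Xr is, and only in women initially ZIKV IgG-negative. Women already cross-reactive at baseline are outside the denominator.
- **That 8.1.4 is the fixed input to the VTR correction.** 8.1.7 names no source and 8.2.1 allows 8.1.6 instead. That weakens the link but offers no safe route, since 8.1.6 is worded the same way.
- **That the ZIKV prior would move against section 5.4**, where a ZIKV IgM-positive result is "more likely to be a DENV infection if large numbers of DENV are being reported". Weekly trends come from virus-specific surveillance counts. The prior would track DENV only if a contaminated theta(t) were applied period by period, and 8.1.7 plans to check whether theta(t) is stable.
- **That a VTR bias of a given size is demonstrated.** The calculation is a single-test illustration. Section 7.6 wants adjustment on the whole algorithm, with confirmatory tests, and Appendix 2 models DENV explicitly for doubly positive samples.

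**Conclusion.** The point holds as an inconsistency with a predictable direction of bias. Neither incidence route expressly commits to a cross-reactivity adjustment, and 8.1.4 has no equation that could apply one to seroconversions. Following the text literally biases incidence upward and mean IgM persistence downward; the persistence effect is the firmer one, because 8.2.1 names its sources. The effect on VTR is conditional on which incidence estimate enters 8.1.7.

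The size cannot be fixed from the SAP. Under the assumed ranges it can be large when ZIKV risk is low relative to DENV (VTR 0.28 to 0.96 of its proper value at 1% risk, 0.58 in the central case). It is modest at 10% risk (0.87 to 1.00, central 0.97). If the specificity used were an effective value specific to center and season that already included cross-reaction, part of this would be absorbed. The change should be made, since section 7.6 itself treats low incidence as the setting where false positives matter most.

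**What to change.** 1. **8.1.4.** State that the adjusted estimate includes ZIKV-DENV cross-reactivity, and model the two viruses jointly in women initially IgG-negative for the virus concerned, for example

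   P(Z seroconversion) = I_Z·Se_Z + (1 − I_Z)·[I_D·Xr_Z + (1 − I_D)·f_Z],

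   with the mirror equation for DENV. I_Z and I_D are infection risks within the woman's own test interval. f_Z is the probability of a false seroconversion given a negative baseline test. It should not simply be set to the cross-sectional 1 − Sp, because section 5.4 expects strong correlation between repeat tests of the same type.
2. **8.1.6.** State that it uses the cross-reactivity-adjusted cumulative incidence of 8.1.2.
3. **8.1.7 and 8.2.1.** State that only cross-reactivity-adjusted incidence is used, and name which estimate (8.1.4 or 8.1.6) feeds each.
4. **Reporting.** Keep the term *crude* for unadjusted figures, as 8.1.2 defines it, and show the sensitivity-specificity-only estimate as a sensitivity analysis.

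The cost is SAP wording and one more equation in the Bayesian framework already planned in 8.3. The SAP already expects Xr from ZIKA-VID, with vague priors where it is lacking (Appendix 6). Incidence intervals will be somewhat wider.

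### Section 8.1.6 would read a shift in recruitment area within a center as a change in incidence, because it compares adjusted seroprevalence in different women without holding the area mix fixed

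*SAP*

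**What the plan says.** SAP section 8.1.6 is titled "Incidence of primary infections estimated by increase in seroprevalence". If cumulative incidence π is known or can be estimated at a starting point T, "then cumulative incidence at time t is related to incidence between t and T as follows":

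π(t) = π(T) + (1 − π(T))·(1 − exp(−Σλ(u)))

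A second version, suggested for DENV, adds age. The only assumption the section states concerns test accuracy: "These calculations assume that cumulative incidence can be estimated by adjusting seroprevalence for sensitivity and specificity".

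The input comes from 8.1.2. Its denominator is the women with at least one IgG test, and "the numerator is the number who were IgG+ on their first test".

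On recruitment, 8.1 says that within each center "the intention is to recruit pregnant women from areas at higher risk of arbovirus infection, and during periods of higher incidence". It concludes that estimates of incidence and seroprevalence taken directly from the study "are not true population estimates". On stratification it says: "All analyses will be initially stratified by center and mosquito season, or by center and year if there is no mosquito season". Section 8.1.1 lists, as further demographic breakdowns, "area of residence, residence stratified by arbovirus infection incidence (from surveillance data), as considered appropriate". Section 8.1.6 does not use these variables.

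Two later sections can use the result. Section 8.1.7 turns an incidence estimate into the proportion of infections reported, θ(t), which may then feed the adjustments for gestational age at infection and vertical transmission rate. Section 8.2.1 divides IgM prevalence by incidence, from either 8.1.4 or 8.1.6, to get average IgM persistence.

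**The concern.** The equation is an identity for one fixed population followed from T to t. The data are successive cross-sections of newly recruited women. If a center draws a larger share from high-seroprevalence areas at t than at T, pooled seroprevalence rises with no one newly infected, and λ is the only term available to absorb the rise. A move the other way pushes the estimate down.

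The safeguards in the text do not address this:

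- Stratifying by center and season separates the dates being compared. It does not hold area constant within a center.
- The sensitivity and specificity correction acts on each date separately and leaves a difference in mix in place.
- The caveat in 8.1 concerns the level of the estimates. It does not say that a change over time may be an artefact of who was recruited.

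At stake is any later quantity that takes its incidence from 8.1.6: θ(t) in 8.1.7, through it the absolute a priori risk that section 7.6 needs, and the persistence check in 8.2.1.

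**Working it through.** The SAP gives no figure for 8.1.6, so there is none to reproduce.

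**Inputs.** The identity is from 8.1.6 and θ(t) = M(t) / [N(1 − exp(−λ(t)))] is from 8.1.7. Area-specific cumulative incidence and recruitment shares are not in the SAP. Those used here are assumptions, shown over a range.

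**Step 1: invert the identity.** With Λ = Σλ(u), Λ = −ln[(1 − π(t)) / (1 − π(T))]. Check on a closed cohort: π(T) = 0.40 and Λ = 0.10 give π(t) = 0.457, and inversion returns 0.100. The identity is sound for a fixed population.

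**Step 2: two areas, no new infections, only the mix changes.** Pooled π = w·π_high + (1 − w)·π_low, where w is the share recruited from the high-risk area.

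| Areas (low / high) | w at T → t | π(T) → π(t) | Λ returned (true value 0) |
|---|---|---|---|
| 5% / 10% | 50% → 60% | 0.075 → 0.080 | −ln(0.920/0.925) = 0.005 |
| 20% / 40% | 50% → 60% | 0.300 → 0.320 | −ln(0.68/0.70) = 0.029 |
| 20% / 40% | 50% → 80% | 0.300 → 0.360 | −ln(0.64/0.70) = 0.090 |
| 20% / 60% | 50% → 70% | 0.400 → 0.480 | −ln(0.52/0.60) = 0.143 |
| 20% / 60% | 20% → 80% | 0.280 → 0.520 | −ln(0.48/0.72) = 0.405 |
| 20% / 40% | 80% → 50% | 0.360 → 0.300 | −ln(0.70/0.64) = −0.090 |

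**Step 3: does the accuracy correction help?** Take 20%/40%, 50% → 80%, with sensitivity and specificity both 0.95 (assumed). Observed seroprevalences are 0.320 and 0.374. Corrected, they return to 0.300 and 0.360, and Λ is again 0.090. The artefact is unchanged.

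**Step 4: with true infection.** If both areas share a true Λ of 0.05, then 1 − π(t) is the mix-only value times exp(−0.05), so the artefact adds to the truth. For areas at 20%/40%:

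- w held at 50%: estimate 0.050, correct.
- w 50% → 60%: 0.050 + 0.029 = 0.079. θ(t) relative to truth is (1 − e^−0.05)/(1 − e^−0.079) = 0.0488/0.0760 = 0.64.
- w 50% → 80%: 0.050 + 0.090 = 0.140, and θ(t) is 0.37 of truth.
- w 60% → 50%: 0.050 − 0.029 = 0.021, an underestimate.

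In 8.2.1, dividing by 0.079 instead of 0.050 would give an average IgM persistence 0.050/0.079 = 0.63 of the true value.

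**Step 5: after the change.** Fitted within area, the zero-incidence data of Step 2 give Λ = 0 in each area in every scenario.

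**The case against.** The strongest reply is that the trigger is not in the document. A constant targeting rule biases the level of seroprevalence, not its change, and the SAP nowhere says the area mix within a center will move between dates. This stands: the bias is conditional. Section 8.1 does describe recruitment steered by area and period, and section 10.3 foresees possible targeted recruitment of women with specific risk factors after a sample size review, so a shift is foreseeable; but it is not planned.

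Second, stratification by center and season is only initial, 8.1.6 presents its model as an example, and the breakdowns in 8.1.1 could reveal a shift. This also stands in part. The plan permits area strata, but does not call for them here.

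Third, there are partial safeguards. Section 8.1.4 estimates incidence from seroconversion within the same woman, which a change in mix cannot create. Section 8.1.7 proposes examining θ(t) for stability, and a spurious rise in incidence would lower it; but a real change in reporting could look the same. Section 8.2 calls its analyses supportive and leaves the definitive persistence estimate to 7.5.

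Fourth, negative values come from algebraic inversion. A model that constrains λ to be non-negative would not return them, though the estimate would still be biased downward.

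A reader might infer that the spurious attack rate becomes an individual woman's prior probability in the false-positive correction and so directly distorts the vertical transmission rate. The documents do not support that. Section 8.1.7 does not name 8.1.6 as its source of incidence. Section 5.4 takes time trends from surveillance and uses study data only for an approximate reporting proportion. Section 7.6 requires the correction to reflect the entire testing algorithm and the full set of results.

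**Conclusion.** The point holds in conditional form. Section 8.1.6 is valid only if the recruited mix is constant between T and t. The SAP does not state this assumption, and neither the initial stratification nor the accuracy correction secures it. If the area mix within a center shifts, the shift is read as incidence or biases it downward.

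The size depends wholly on assumed area contrasts and shares. With no true infection, Λ runs from 0.005 for a small contrast and shift to 0.405 for large ones, so small shifts do little and moderate ones matter. Against a true Λ of 0.05, a shift of ten percentage points between areas at 20% and 40% gives 0.079 and puts θ(t) at 0.64 of truth.

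The consequence reaches only as far as 8.1.6 incidence is actually used in 8.1.7 (and through it in 7.6) or in 8.2.1. The SAP leaves this open, giving no preference between 8.1.4 and 8.1.6. The text does not support saying that the mix will shift, or that the main vertical transmission estimate is biased by this route.

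**What to change.** In section 8.1.6:

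- State that the method assumes a constant recruitment mix between T and t.
- Fit the model within strata of area of residence, or of residence by surveillance incidence, both already listed in 8.1.1. Give each stratum its own π(T) and use only strata sampled at both dates. Alternatively, standardise both dates to a fixed area and age mix.
- Show the pooled version only beside the stratified or standardised one.
- Compare the result with the within-woman estimate of 8.1.4 for the same center and period. Where they disagree, use 8.1.4 as the input to 8.1.7 and 7.6.

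The cost is some SAP wording, a stratified model and somewhat wider intervals; the variables are already planned. Shifts in mix within a stratum would remain, which is a further reason for the comparison with 8.1.4.

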## 2.2 Objectives relating to the population epidemiology of ZIKV, DENV and CHIKV

- (i) The incidence and cumulative incidence of arbovirus infections in areas contributing data; the prevalence of co-infections; impact of previous infections
- (ii) The proportion of infections that are symptomatic, and the impact of previous infection with the same or other arboviruses.
- (iii) Alignment with national or regional surveillance data, to obtain population estimates of national or regional incidence of ZIKV, DENV, CHIKV whether symptomatic or not.

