#### 8.2 Analyses of properties of diagnostic tests

As noted earlier the ZIKA-VT and ZIKA-VID programs are inter-related and the analyses set out in *Section 7.5* will provide the definitive information on the persistence of IgM and other tests.

However, the population epidemiology data collected by ZIKA-VT also provides an opportunity for *supportive* analyses of test persistence, sensitivity and specificity. Results should be compared with the more formal evaluations undertaken as part of ZIKA-VID, which will comprise evidence from published literature as well as findings from *de novo* field work.

8.2.1 Average persistence of IgM. Given estimates of IgM prevalence (section 8.1.5) and incidence of primary infections based on seroconversion (section 8.1.4) or changes in cumulative incidence (section 8.1.6), estimates of the average persistence of IgM can be estimated by dividing IgM prevalence by IgM incidence.

We anticipate that IgM persistence may differ in women with previous ZIKV or DENV infections. If these women can be identified by avidity tests it will be possible to generate separate estimates of average IgM persistence for primary and secondary infections

8.2.2 Sensitivity and cross-reactivity of IgM and IgG tests. Estimates of sensitivity will be available for IgM and IgG tests in women with infections confirmed by PCR, and from cases where tests failed to detect infections in mothers of babies in whom congenital infection is demonstrated.

8.2.3 Specificity of IgM and IgG tests. Specificity of IgG tests can only be estimated in populations which are known to have not been exposed to the infection in question: this means that data collected in ZIKA-VT is not relevant to estimates of IgG specificity. However, IgM specificity can be studied by observing the relationship between the proportion of tests which are positive and the surveillance data over the previous 12 months. IgM persistence is believed to be about 12 weeks on average, so that an IgM+ occurring at a time when surveillance sources indicate there has been no virus circulating for over 4 or 5 months are highly likely to be false positives from a diagnostic point of view, whether due to persistent antibody, cross-reactions, or other factors; although it will be important to be able to rule out foreign travel before making these inferences. Data of this sort will be of great importance in defining the tails of the persistence distributions of IgM tests

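### The age-specific DENV equation in SAP 8.1.6 is mis-indexed: with a read as current age, it compares two birth cohorts and returns zero incidence under steady endemic transmission

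*SAP*

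**What the plan says.** Section 8.1.6 of the SAP is headed "Incidence of primary infections estimated by increase in seroprevalence". After an equation without age, it adds an age-specific version for dengue: "For DENV infection, which has been present for much longer, it may be preferable to model age-and time-specific cumulative incidence". In plain notation the printed equation is

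`pi(a,t) = pi(a,T) + (1 - pi(a,T)) * (1 - exp(-sum over T<=u<=t of lambda(a-T+u,u)))`.

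On the age range it says "Using data from pregnant women, we would model incidence from time T and age 16 upwards". It does not say whether a is age at T, age at t or age at test.

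The data behind pi are described in section 8.1.2: the denominator is women with at least one IgG test, and "the numerator is the number who were IgG+ on their first test". These are successive cross-sections of recruits, not one group retested. Section 2.2 makes the result an objective: "The incidence and cumulative incidence of arbovirus infections in areas contributing data".

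**The concern.** The two sides of the equation appear to describe different women. The hazard term starts at age a when u=T and reaches age a+(t-T) when u=t, so it follows the cohort aged a at T. The left side carries the unchanged age a at the later date t. Read as age at t, that is a cohort born t-T years later. The equation then omits the t-T years of exposure that separate pi(a,T) from pi(a-(t-T),T).

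This matters most where transmission is long established, and that is the reason the SAP gives for using the age-specific form for DENV. Section 8.2.1 names 8.1.6 as one possible source of incidence, and there "estimates of the average persistence of IgM can be estimated by dividing IgM prevalence by IgM incidence". Section 8.1.7 divides reported cases by `N(1 - exp(-lambda(t)))` to obtain the reporting fraction. An incidence estimate of zero leaves both quantities undefined.

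**Working it through.** The SAP gives no numerical result here, so there is no figure to reproduce. The check is to invert the equation and apply it to known situations.

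**Inputs.** The equation is from section 8.1.6 and the first-test data are from 8.1.2. The hazards, age 25 and the gaps between dates are assumptions, because the SAP gives none.

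**Step 1: invert.** Since `1 - pi(a,t) = (1 - pi(a,T)) * exp(-sum lambda)`,

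`sum lambda = -ln[(1 - pi(a,t)) / (1 - pi(a,T))]`.

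**Step 2: steady endemic state, a read as current age.** With a constant hazard since birth, `pi(age) = 1 - exp(-lambda*age)` at every date. So pi(25,t) = pi(25,T), the ratio is 1 and the sum is 0. With the left side written as pi(a+t-T,t), the same inversion recovers the true value. For t-T = 2 years:

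| Assumed lambda per year | pi(25), both dates | pi(27) at t | True sum | As printed, a = current age | Left side pi(a+t-T,t) |
|---|---|---|---|---|---|
| 0.02 | 0.394 | 0.417 | 0.04 | 0 | 0.04 |
| 0.05 | 0.713 | 0.741 | 0.10 | 0 | 0.10 |
| 0.10 | 0.918 | 0.933 | 0.20 | 0 | 0.20 |

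Gaps of 1 and 4 years behave the same way: zero as printed, and the true value with the cohort index. The zero does not depend on the assumed hazard.

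**Step 3: hazard changes at T, 2-year gap, age 25.** Let the hazard be l0 before T and l1 after it. Women aged 25 at t have lifetime exposure `23*l0 + 2*l1`. Women aged 25 at T have `25*l0`. The printed equation returns the difference, `2*(l1 - l0)`, whereas the true sum is `2*l1`.

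| l0 to l1 | Exposure, aged 25 at t | Exposure, aged 25 at T | Returned | True |
|---|---|---|---|---|
| 0.05 to 0.10 | 1.35 | 1.25 | 0.10 | 0.20 |
| 0.10 to 0.05 | 2.40 | 2.50 | -0.10 | 0.10 |
| 0.05 to 0 | 1.15 | 1.25 | -0.10 | 0 |

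A negative cumulative hazard is impossible. With the cohort index, all three rows return the true value.

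**The case against.** The strongest reply is that a may be a cohort label, age at T. Every term on the right is then correct, the left side is that cohort's cumulative incidence at t, and the equation is right. The ageing of the hazard argument makes sense only if a cohort is being followed, and modelling from time T and age 16 upwards fits cohorts aged 16 or more at T. This stands as a possible reading, and it shows that the right side needs no change.

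It does not rescue the text as it is. The SAP calls pi age- and time-specific, and in the same equation the first argument of lambda is age at the stated date. First-test results would naturally be tabulated by age at test. An analyst who entered those values as pi(a,t) and pi(a,T) would get the error.

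The other replies limit the consequences, and they stand:

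- The wording "it may be preferable to model age-and time-specific cumulative incidence" makes the model optional.
- Section 8.1.4 estimates incidence of primary infection directly from seroconversions over time at risk.
- Section 8.2.1 accepts either source, and section 8.2 calls such analyses supportive.
- Section 8.1.7 does not name 8.1.6 as its source.
- A zero DENV estimate beside observed seroconversions would be noticed. A halved one, as in the row for 0.05 to 0.10, might not be.

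**Conclusion.** The equation is wrong under its natural reading, and its key index is undefined under any reading. Applied to first-test seroprevalence by current age, it measures the difference in lifetime exposure between two birth cohorts. That is zero in a steady endemic state and negative if incidence has fallen. The zero follows algebraically from pi(a,t) = pi(a,T). The other figures rest on the assumed hazards, age 25 and the 2-year gap.

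The effect is confined to DENV incidence taken from 8.1.6 and to its uses: IgM persistence in 8.2.1 and, if this is the source chosen, the reporting fraction in 8.1.7.

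A reader might infer that the plan will certainly report zero DENV incidence, or that the error carries through section 7.6 and Appendix 2 into the vertical transmission rate. The documents support neither. The zero depends on how a is read. Sections 7.6 and Appendix 2 need an absolute incidence, but nothing ties them to this equation alone. The point is a low-cost correction to make before the model is coded, and it does not invalidate the incidence analyses as a whole.

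**What to change.** Use one of two equivalent forms and state what a means.

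1. **a is age at T.** Keep the right side and write the left side as `pi(a+t-T,t)`. Women under 16 at T are left out of this calculation, and no extrapolation is needed.
2. **a is age at t.** Write `pi(a,t) = pi(a-t+T,T) + (1 - pi(a-t+T,T)) * (1 - exp(-sum over u of lambda(a-t+u,u)))`. Give the baseline a smooth age curve or a prior only where a-t+T is below 16.

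In either case, state that first-test results are matched by birth cohort and not by age at test. The cost is one equation, one definition and the matching model code, with no new data collection. Form 1 loses the women who were under 16 at T. Form 2 keeps them but needs an assumption about baseline prevalence below 16.
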